PRIMARY OBJECTIVE	We will test the hypothesis that 1 month of treatment with INI (40 IU q.i.d.), with the SGLT2i empagliflozin (empa; 10 mg q.d.), and with combined insulin plus empagliflozin (INI+empa) will result in safety profiles (number of treatment-related serious adverse events/primary outcome) that are similar to placebo.
SECONDARY OBJECTIVES	We will determine the effects of singular and combined therapy on AD cerebrospinal fluid biomarkers, cerebral blood flow (CBF) and cognition.
PRIMARY OUTCOME MEASURE	Number of treatment-related serious adverse events
SECONDARY OUTCOME MEASURES	PACC5, ADAS-Cog14, CSF A $\beta$ 40, A $\beta$ 42, total tau, and phospho-tau 181, whole brain CBF
STUDY DESIGN	Single-site, double-blind study
SAMPLE SIZE	n=60
SUMMARY OF KEY ELIGIBILITY CRITERIA	
 
Cognitively normal with positive amyloid (amyloid PET SUVR>1.21, CSF A<math>\beta</math>42<600 pg/ml)
 
Diagnosis of amnestic mild cognitive impairment (MCI) or early AD (CDR 0.5 or 1, MMSE>21)
 
Age: 55 to 85 years (inclusive)
 

DRUG DOSAGE & FORMULATION	40 International Units Humulin® R U-100 (Eli Lilly, Inc.) q.i.d.; empagliflozin (10 mg q.d.)
DURATION OF PARTICIPATION	8 weeks (4 weeks on active treatment)
PLACEBO	Insulin diluent (Eli Lilly, Inc.); cellulose capsule

ROUTE OF ADMINISTRATION	Intranasal (insulin); oral (empagliflozin)
PROCEDURES	Physical and neurological exam, nasal examination, cognitive testing, magnetic resonance imaging (MRI), continuous glucose monitoring, actigraphic sleep assessment, lumbar puncture, vitals, clinical labs, CSF and blood analysis and banking and APOE genotyping.

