### 3.4 Statistical Analyses

[figure not shown]
For the intent-to-treat (ITT) sample, co-primary (delayed story recall and DSRS) and secondary (ADAS-Cog and ADAS-ADL) scores were log transformed. Scores were first subjected to mixed model repeated ANCOVA including all treatment groups (placebo, low dose insulin or high dose insulin) as the between subjects factor, and time (baseline, month 2, month 4) as the repeated factor using the SAS v9.2 General Linear Models procedure. After a significant ( $p<0.05$ ) time by treatment group interaction reflecting a different pattern of change, each of the two insulin groups was compared separately with the placebo group using repeated measures ANCOVAs. Effect sizes (Cohen's  $f^2$ ) were calculated for all significant effects. Age was included as a covariate in all analyses. Diagnosis (aMCI or AD), gender, APOE- $\epsilon$ 4 carriage status (yes or no), baseline 3MSE score, and years of education were also included as covariates. Non-significant covariates were dropped from the model. Significant relationships with covariates were explored with Pearson correlation (continuous variables) or follow-up ANOVAs (class variables). Missing values were treated with multiple imputation (Rubin 1987). For exploratory CSF biomarker analyses, because only a subset of participants elected to undergo LP and no differences were observed between the two insulin dose arms, the groups were combined into a single insulin-treated group to maximize power. Biomarkers were analyzed with the repeated ANCOVA strategy described above and, due to the small sample size, exploratory Spearman correlations were conducted to examine relationships among changes in biomarkers and outcome measures. Only study completers underwent post-treatment FDG-PET. Pre and post treatment scans were co-registered within subject and anatomically standardized to Talairach and Tournoux stereotactic coordinates (Talairach and Tournoux 1988, Minoshima, Koepp et al. 1994). Pixel intensity was normalized to pontine values (Minoshima, Frey et al. 1995). Interval regional CMRglc changes within groups were assessed using voxel-wise one-sample t statistics (pre-/post-treatment pair) and probability integral conversion to z scores (Worsley, Evans et al. 1992). Interval changes in regional CMRglc were then compared between 1) low insulin vs. placebo groups, and 2) high insulin vs. placebo groups. Based on the number of voxels and smoothness of the statistical map, a Type I error rate was controlled at 0.05 to account for multiple comparisons (Worsley, Evans et al. 1992). The resulting statistical maps were visualized in three-dimensional stereotactic surface

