## **6.0 STUDY OVERVIEW**

The study will consist of a single site, randomized, double-blind trial comparing the effects of 4 weeks of INI (40 International Units q.i.d.), empa (10 mg q.d.) and combined INI and empa compared with placebo on CSF biomarkers and cognition. At study entry, participants will be randomized to one of 4 conditions: INI, empa, INI+empa, placebo. Participants who are cognitively normal but have abnormal elevations of brain amyloid (n=20) or who have MCI or early AD (n=40) will be enrolled. The primary outcome measure will consist of safety (treatment-related serious adverse events). Secondary measures will consist of CSF biomarkers, cognition, and cerebral blood flow. Exploratory measures will include continuous glucose levels and sleep quality as assessed with actigraphy.

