### **6.1 Study Population**

A total of 60 adults who are 1) cognitively normal/amyloid positive (n=20) or 2) diagnosed with aMCI or early AD (n=40) will be enrolled in this trial. To determine eligibility, all participants will undergo cognitive assessment, physical and neurological examination, ECG, clinical/safety laboratory assessment, and interviews of the participant and study partner conducted by the investigators and staff of the Clinical Core of the Wake Forest Alzheimer's Disease Research Center (ADRC).

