## **12.0 STATISTICAL PLAN**

Statistical analyses will be conducted by the ADRC Biostatistics Core. To address the Primary Aim, number of treatment-related SAEs will be subjected to a repeated measures analysis of variance with group and time as the repeated measures. Secondary analyses will examine the effect of diagnostic status (cognitively normal vs. MCI/AD). Secondary analyses will also examine treatment-related differences for other CSF and plasma biomarkers, cognitive scores, and whole brain cerebral blood flow.

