## **15.2 Randomization**

Eligible participants will be randomized on a 1:1 schedule to placebo (insulin diluent; placebo capsule), INI, empa, or INI+empa. Randomization will be stratified by diagnosis (normal, MCI or AD)

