## **16.2 Following Up on AEs**

The investigator is obliged to follow participants with AEs until the events have subsided, the conditions are considered medically stable, or the participants are no longer available for follow up. Participants who discontinue due to adverse experiences will be treated and followed according to established medical practice. Adverse events will be rated as mild, moderate or severe. This will also pertain to abnormal laboratory values deemed clinically significant by the site clinician.

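### The primary SAE count is assigned to a repeated-measures ANOVA with no analysis set or early-exit rule, so a complete-case run could drop a participant together with the SAE that ended participation

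*Combined protocol and SAP*

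**What the plan says.** One sentence in section 12.0 covers the primary aim: the number of treatment-related SAEs is to be "subjected to a repeated measures analysis of variance with group and time as the repeated measures". The hypothesis, in the synopsis that follows the glossary, is "safety profiles (number of treatment-related serious adverse events/primary outcome) that are similar to placebo". Section 15.2 has participants "randomized on a 1:1 schedule to placebo (insulin diluent; placebo capsule), INI, empa, or INI+empa", so each person belongs to one group only.

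Section 12.0 does not define the levels of time, say whether the model is classical or mixed, name the participants to be analysed, or deal with early exit. For this trial, intent-to-treat appears only as a glossary abbreviation. Section 12.1 reports no power calculation.

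Three other sections bear on the point:

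- Section 16.2 foresees exits: "Participants who discontinue due to adverse experiences will be treated and followed according to established medical practice". It gives no analysis rule for them.
- Section 17.2 captures SAEs at any time after consent, whether or not drug was taken. Section 20.4 follows them to resolution or for 90 days after participation ends.
- Section 3.4 describes the earlier pilot study, with an ITT sample, time "as the repeated factor using the SAS v9.2 General Linear Models procedure", and "Missing values were treated with multiple imputation". Section 12.0 adopts neither the ITT sample nor the imputation.

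**The concern.** Classical repeated-measures ANOVA needs a value in every time cell. A participant with a gap is removed completely, including the periods that were observed. For an SAE count the event itself may cause the gap, so the exclusion can depend on the outcome. Because the hypothesis is similarity, events lost from the active arms would favour the hoped-for conclusion.

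This is separate from the lack of a criterion for similarity, since a margin would not restore deleted participants. The method also suits the outcome poorly in other ways. The data are a rare count, nearly all zeros; group cannot be a repeated measure in a parallel design; and the aim concerns how many SAEs occur, not their course over time.

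**Working it through.** The plan states no SAE rate, dropout rate, alpha or margin for this trial, so there is no figure to reproduce. N = 60 (section 6.1) with equal allocation to four arms (section 15.2) gives 60/4 = 15 per arm. All rates in steps 2 to 4 are assumptions.

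**1. Deletion of single cases (needs only the arm size; Clopper-Pearson 95% intervals).**

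- One SAE exit: 1/15 = 6.7% (0.2 to 31.9%) becomes 0/14 = 0% (0 to 23.2%).
- Two SAE exits: 2/15 = 13.3% (1.7 to 40.5%) becomes 0/13 = 0% (0 to 24.7%).

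**2. Expected rate in one arm.** Let p be the SAE risk and q the chance that a participant with an SAE leaves and is deleted. The analysed rate is p(1−q)/(1−pq). At p = 10%:

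- q = 25%: 0.075/0.975 = 7.7%
- q = 50%: 0.05/0.95 = 5.3%
- q = 100%: 0%

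The chance that an arm of 15 with at least one SAE shows none is [(1−p(1−q))^15 − (1−p)^15] / [1 − (1−p)^15]. At p = 10%:

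- q = 25%: (0.311 − 0.206)/0.794 = 13%
- q = 50%: (0.463 − 0.206)/0.794 = 32%
- q = 100%: 100%

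**3. Expected difference, active minus placebo (points), same q in every arm.**

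| True rates | q=0 | q=25% | q=50% | q=75% | q=100% |
|---|---|---|---|---|---|
| 10% v 2% | 8.0 | 6.2 | 4.3 | 2.2 | 0 |
| 20% v 2% | 18.0 | 14.3 | 10.1 | 5.4 | 0 |

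For example, at 10% against 2% and q = 50%: 0.05/0.95 − 0.01/0.99 = 5.26% − 1.01% = 4.3 points. If everyone is counted with all SAEs up to exit, the difference stays at 8.0 or 18.0 points whatever q is.

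**4. Effect on the test.** A simulation used 5,000 trials of 4 × 15, with the group test taken as a one-way ANOVA on participant totals among completers and p < 0.05 assumed as the threshold. It gave a significant result in about 7%, 2.5% and 0% of trials at q = 0, 50% and 100% for 10% against 2%. For 20% against 2% the figures were about 19%, 9% and 0%.

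**5. Direction is not fixed.** Suppose one SAE in an active arm and one on placebo: 1/15 against 1/15, a difference of 0. If only the placebo case leaves and is deleted, the comparison becomes 1/15 against 0/14, a difference of 6.7 points. With equal rates and equal q, the expected difference stays at 0.

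**6. Without any deletion** the comparison is already weak: 0/15 is compatible with a true rate up to 21.8% (1 − 0.025^(1/15)), and 4/15 against 0/15 gives Fisher p = 0.10.

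**The case against.** The strongest reply is that section 12.0 does not say what the mechanism requires. A reader might infer a visit-by-visit analysis that needs complete visits. Section 20.4 does ask about SAEs at each visit, which makes visit a plausible time unit, but the plan states neither the unit nor a completeness requirement. A mixed model, or zeros entered for intervals after exit, would keep every participant.

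Nor is a missed visit a missing SAE. Sections 17.2 and 20.4 record SAEs independently of attendance and follow them after exit, and section 16.2 obliges the investigator to follow participants with adverse events, so it does not describe loss to the study.

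A reader might also take the pilot as evidence of listwise deletion. It is unclear evidence: the sentence in section 3.4 that names the General Linear Models procedure calls the model mixed. It also concerns cognitive and functional scores, whereas section 3.8 reports the pilot's adverse events as group totals and means.

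Finally, a reader might infer that the error always favours the sponsor's conclusion. It does not. Deletion applies to placebo too, where related SAEs can occur because section 20.4 grades relatedness to participation or procedure and no arm is exempt from lumbar puncture. The pilot also saw no treatment-related SAEs in 4 months, so the 10% and 20% rates are illustrations, not forecasts.

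All of this stands, and it makes the point conditional. It does not remove it: nothing commits the primary analysis to the recorded SAEs of everyone treated, and the one method named has a standard form that can discard them.

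**Conclusion.** The point holds in conditional form. The plan names an ill-suited method for its primary outcome and leaves open who is analysed and how early exits are treated. If run as a complete-case analysis, it could drop participants whose SAE ends participation. The pull towards similarity is an average effect that needs two conditions: truly higher active-arm rates, and SAE cases who leave.

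The documents do not allow its size to be computed. From the arm size alone, one deletion moves an arm from 6.7% to 0%. Under the assumed 10% against 2% rates, between none and all of an 8.0-point difference is lost as q runs from 0 to 100%. The documents do not support saying that the plan requires complete visits or that its primary result is biased. They do support saying that the plan fails to rule this out when it could do so at almost no cost.

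**What to change.** In section 12.0, replace the repeated-measures ANOVA for the primary outcome with the following:

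- One value per participant.
- An analysis set of every randomised participant who received at least one dose.
- All treatment-related SAEs from first dose to the end of follow-up, counted whether or not later visits were attended.
- By arm, the number and proportion with at least one event, with exact 95% confidence intervals, and the difference of each active arm from placebo.

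Any pattern over time can be listed descriptively.

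The text should state when follow-up for new events ends, identically for all arms, because section 20.4 gives a period for following SAEs but section 12.0 gives no counting window. Two conflicts must be reconciled before the count is defined: section 5.2 describes the primary outcome as treatment-related adverse events without requiring seriousness, and section 1.1 gives 4 months of treatment where the synopsis gives 1 month and section 6.0 gives 4 weeks.

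The cost is SAP wording. No added visit, assessment or participant is needed, and the result no longer depends on who leaves after an SAE. The same edit removes the ANOVA on a rare count and the mislabelled group factor. It does not supply a criterion for similarity, which remains a separate gap.

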### **12.1 Power Analyses**

As this study is designed as a proof of concept study power calculations have not been conducted.

## **13.0 POTENTIAL RISKS**

### 13.1 Safety of Intranasal Insulin

Safety issues pertaining to INI administration for the treatment of diabetes have been extensively explored for over two decades (Pontiroli, Alberetto et al. 1982). For diabetes treatment, absorption enhancers must be used to increase the transport of insulin across the nasal membrane to the periphery due to the fact that peripheral bioavailability of insulin without absorption enhancers is less than 1% (Illum 2002). A recent safety study of INI administration without absorption enhancers demonstrated no treatment induced changes in blood glucose levels, nasal airway patency, or transnasal pressure gradient (Kupila, Sipila et al. 2003). There are no known serious risks associated with INI without enhancers. A recent industry report raised the issue of rare but significant increases in lung cancer in smokers treated with inhaled insulin; six of 4740 patients taking inhaled insulin developed lung cancer compared with one of 4292 patients who received an active comparator (incidence per 100 patient years exposure, 0.13 vs 0.02). However, the inhaled insulin protocol used for diabetes treatment in this report included absorption enhancers to maximize delivery to lungs, whereas the nose-to-brain delivery device to be used in this study greatly minimizes lung delivery.

Regarding the risk of hypoglycemia, at least five peer reviewed human studies (Kern, Born et al. 1999, Born, Lange et al. 2002, Kupila, Sipila et al. 2003, Benedict, Hallschmid et al. 2004, Stockhorst, de Fries et al. Submitted for publication) and four preliminary studies (Reger, Watson et al. 2006, Reger, Watson et al. 2008, Reger, Watson et al. 2008) (Craft, Baker et al. 2012) revealed no change in blood glucose levels following intranasal insulin administration with doses that included 40 International Units 4 times daily for two months. There was one exception with the case of a single participant who experienced mild hypoglycemia (52 mg/dl) after skipping a meal and engaging in sustained vigorous exercise. In addition, a recent safety study (Kupila, Sipila et al. 2003) examined intranasal insulin administration of 60 International Units once a day for three weeks in 21 healthy adults. This randomized, double-blind, placebo-controlled crossover trial measured blood glucose levels six times a day during the first two and the last two days of treatment. Pre- and post-treatment blood laboratory tests and nasal examinations were performed. The nasal studies included rhinoscopy to detect local irritation, a saccharin particle test to analyze mucociliary clearance, and rhinomanometry to evaluate nasal airway patency and transnasal pressure gradient. Results indicated no change in blood glucose values with insulin, and no change in the frequency of glucose values above 3.0 mmol/L.

The only symptomatic hypoglycemic value occurred during placebo treatment. Insulin treatment had no effect on other laboratory values (C-peptide, total cholesterol, HDL, LDL, triglycerides, creatinine, glutamyl transferase), blood pressure, or body weight. In addition, nasal examinations revealed no adverse effects or functional disturbances following intranasal insulin administration. No serious adverse effects of treatment were observed in the preliminary studies (Reger, Watson et al. 2006, Reger, Watson et al. 2008, Reger, Watson et al. 2008, Craft, Baker et al. 2012).

### 13.1 Safety of empagliflozin

SGLT2is including empagliflozin has been studied in multiple large trials of adults with Type 2 diabetes, as well as in non-diabetics with cardiovascular disease, and generally found to be safe (for a review, see Scheen, Nature, 2020). They are now considered standard of care for Type 2 diabetic patients with cardiovascular disease. Adverse effects that have been reported include: genital yeast infections especially in females, volume depletion, and diabetic ketoacidosis in the subset of Type 2 diabetic patients who have reduced insulin secretory capacity. Other effects may include frequent urination. Adults with seriously compromised kidney function (eGFR<45 mL/min/1.73m^2) are not advised to take empa; kidney function will be assessed at the screening visit. Hypotension may also be observed rarely in patients with low systolic blood pressure, or who are taking diuretics. Participants will be monitored for hypotension and/or associate symptoms at each visit and during the two phone safety/compliance calls.

### **13.2 Safety of combined insulin and empagliflozin**

Combined therapy of insulin and SGLT2is, including empa, was associated with rare but increased risk of ketoacidosis in the subset of Type 2 diabetic patients who have reduced insulin secretory capacity. Hypoglycemia has also been noted with combined administration, thought to be due to reduced hyperglycemia and related improvement in insulin sensitivity without concomitant reduction in insulin dosing. The proposed study will exclude participants with Type 2 diabetes, and will monitor blood glucose at all visits, as well as with continuous glucose monitoring during the last week of treatment. No other adverse interactions have been noted and SGLT2is are commonly prescribed for insulin-treated diabetics because of the multiple benefits on glycemic control and vascular function (Scheen, *Nature*, 2020).

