### **6.4 Exclusion Criteria**

The following exclusion criteria will be used:

1. A diagnosis of dementia other than AD
2. History of a clinically significant stroke
3. Current evidence or history in past two years of epilepsy, head injury with loss of consciousness, any major psychiatric disorder including psychosis, major depression, bipolar disorder
4. Diabetes (type I or type II) insulin dependent and non-insulin dependent diabetes mellitus
5. Current or past regular use of insulin or any other anti-diabetic medication within 2 months of screening visit
6. History of seizure within past five years
7. Pregnancy or possible pregnancy
8. Use of anticoagulants, unless documentation received from prescribing clinician that anticoagulant medication can be held before LP, and approved by study clinician
9. Residence in a skilled nursing facility at screening
10. Use of an investigational agent within two months of screening visit

11. Regular use of alcohol, narcotics, anticonvulsants, anti-parkinsonian medications, or any other exclusionary medications (exceptions may be made on a case by case basis by study physician)

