### **8.1 Screening (Visit 1)**

The purpose of this visit is to determine study eligibility. Potential participants must sign an informed consent form and HIPAA Authorization prior to administration of any study-related procedures. After consent is obtained, participants will be given the MMSE, the CDR and Story Recall to determine study eligibility. Screening may be waived for participants who have received evaluations from the ADRC within the past 12 months. In addition, all cognitively normal participants must have amyloid PET or CSF Aβ42 results available from the ADRC or affiliated studies prior to screening.

Information regarding demographics, concurrent medications, medical history and adverse events will be gathered from the participant. Vital signs, height and weight will be measured. A brief physical and neurological examination (which include a nasal examination) and a resting ECG will be performed. The ECG report will be reviewed, signed, and dated by the investigator or a medically qualified staff member as delegated by the Principal Investigator. Those with clinically significant ECG findings will be referred for follow-up as deemed appropriate by the investigator. These procedures may be waived for participants who have received evaluations from the ADRC within the past 12-months.

Fasting blood will be drawn for routine clinical laboratory evaluations. If values are outside of the laboratory's normal range and determined clinically significant by the medically qualified study investigators, lab tests may need to be repeated and may be considered exclusionary for participation in the study. Blood samples will also be collected for ApoE genotyping and DNA storage.

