### **8.2 Baseline Visit 1 (Visit 2)**

Results from all screening procedures must be reviewed and all inclusion/exclusion criteria must be met prior to proceeding to baseline. For participants whose screening visit was waived because they had received ADRC evaluations within the past 12-months will sign an informed consent form and HIPAA Authorization prior to administration of any study-related procedures.

According to the randomization schedule, the participant will be assigned to the insulin, empa, insulin+empa or placebo arm. On their first baseline visit they will receive the following:

- 1) Cognitive assessment
- 2) MRI (ADRC MRI may be used if done within 6 months of enrollment)
- 3) Insertion of the Libre Freestyle Pro continuous glucose monitor

- 4) Training on use of the Libre Freestyle Pro continuous glucose monitor
- 5) Training on how to use the intranasal delivery device and provision of saline to use with the device for the 1 week practice period (if applicable)
- 6) Training on how to record compliance
- 7) Training on use of the Empatica E4 actigraph for sleep assessment
- 8) PROMIS Sleep Disturbance and Sleep-Related Impairment Questionnaires
- 9) Patient Health Questionnaire-9 (PHQ-9)
- 10) General Anxiety Disorder Scale (GAD-7)
- 11) Nasal examination
- 12) Vital signs and weight
- 13) Collection of AEs and Con Meds

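### Two safeguards in Section 13 are not carried into the schedule and criteria: no glucose reading at Visit 4, and no eGFR limit in Section 6.4

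*Combined protocol and SAP*

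**What the plan says.** **Glucose.** Section 13.2 (Safety of combined insulin and empagliflozin) notes that hypoglycaemia has been seen when insulin and an SGLT2 inhibitor are given together. As mitigation it says the study excludes type 2 diabetes and "will monitor blood glucose at all visits, as well as with continuous glucose monitoring during the last week of treatment". Table 4 marks blood draws at Visits 1, 3 and 6 and CGM placement at Visits 2 and 5.

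**Kidney.** Section 13.1 (Safety of empagliflozin) says that adults with eGFR below 45 mL/min/1.73m² "are not advised to take empa; kidney function will be assessed at the screening visit". Section 6.4 lists 11 exclusions. Two bear on glucose: "Diabetes (type I or type II) insulin dependent and non-insulin dependent diabetes mellitus" and "Current or past regular use of insulin or any other anti-diabetic medication within 2 months of screening visit". None concerns kidney function. Section 6.3 item 7 requires laboratory values to be normal or, if abnormal, judged clinically insignificant by the study physician.

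**Waiver.** Section 8.1 says, after the examination and ECG, "These procedures may be waived for participants who have received evaluations from the ADRC within the past 12-months". The next paragraph begins "Fasting blood will be drawn for routine clinical laboratory evaluations" and carries no waiver. Section 8.2, however, speaks of the visit as a whole: "For participants whose screening visit was waived because they had received ADRC evaluations within the past 12-months". Footnote 2 of Table 4 also attaches to the whole screening column. Section 8.2 adds a gate: "Results from all screening procedures must be reviewed and all inclusion/exclusion criteria must be met prior to proceeding to baseline".

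**The concern.** These are the protocol's own answers to two risks that it names, and the parts that staff work from day to day do not fully contain them. Staff who follow 13.2 would measure glucose at Visit 4. Staff who follow 8.4 and Table 4 would find nothing there to prompt it. A physician who follows 13.1 has a number to apply to kidney function, but the eligibility list does not contain it.

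The stakes are participant safety and early safety information. Safety is the primary outcome, and Section 5.2 says there is no published safety study of the combination. The dose is 40 IU four times daily, or 160 IU per day. In the sponsor's own pilot (Sections 3.2 and 3.3), at 20 or 40 IU per day, glucose was checked every day in week 1 and once a week after that. The present schedule has less early monitoring at a higher dose, with a second agent added in one arm.

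**Working it through.** No power or alpha calculation is involved. The check sets the commitments beside the schedule, visit by visit. The protocol does not list the routine laboratory panel, so I assume that it includes glucose.

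**Glucose measures (Table 4, Sections 8.1 to 8.7, 10.6, 11.2)**

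- Visit 1: clinical labs.
- Visit 2: CGM placed; before study drug.
- Visit 3: fasting plasma glucose, with blood taken before and after one 40 IU insulin dose. In the listed order, this comes before take-home drug is distributed.
- Visit 4: device review, vial and pill count, re-supply, vital signs, weight, adverse events and medications. No glucose measure. Section 10.2 defines vital signs without glucose.
- Phone call at week 2: adverse events and compliance only.
- Visit 5: CGM placed, recording every 15 minutes for 7 days.
- Visit 6: CGM removed; fasting plasma glucose and clinical labs.

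A blood sample is scheduled at 3 of 6 visits. Counting CGM, 5 of 6 visits have some glucose measure. Visit 4 is the only one with none.

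**Timing (day 0 = dispensing at Visit 3)**

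- Visit 4 is one week later: day 7.
- Treatment lasts 4 weeks = 28 days. If the CGM week is the last treatment week, as 13.2 says, Visit 5 falls at 28 − 7 = day 21.
- First scheduled on-drug glucose data: day 21 as written, day 7 with a Visit 4 reading. Gain: 21 − 7 = 14 days.

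Section 8.6 gives no day for Visit 5, so day 21 rests on the wording of 13.2.

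**Counts (equal allocation assumed)**

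- 60 / 4 = 15 per arm.
- Missing Visit 4 readings: 15 in the combination arm, 60 over all arms.
- Assigned empagliflozin, alone or combined: 2 × 15 = 30.

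**Kidney texts side by side**

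- 13.1 gives a threshold (45) and relies on the screening visit.
- 6.4 contains no renal item.
- 6.3 item 7 is mandatory, but it sets no number and leaves the decision to judgement.
- 6.1 says that every participant has safety labs to determine eligibility. The same sentence lists the cognitive assessment, examination and ECG, which 8.1 expressly allows to be waived on evaluations up to 12 months old. It therefore shows that a result must exist, not that it must be recent.
- On the narrow reading of 8.1, labs are never waived and everyone has new results.
- On the broad reading (8.2 and footnote 2), earlier results may serve. Footnote 3 brings back only consent, demographics and medical history at Visit 2. The next scheduled labs are then at Visit 3, the dispensing visit, and nothing requires those results to be seen before drug is handed out.

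**The case against.** **Table 4 is only an overview.** Section 8.0 calls it that, and it omits other things: Section 10.1 requires a nasal examination at each visit, yet neither 8.4 nor Table 4 lists one at Visit 4. The commitment in 13.2 may therefore still bind, and a fingerstick would not need the blood-draw row. This is fair. It makes the problem a conflict between two parts of the protocol, not proof that no reading would be taken. It also strengthens the case for writing the reading into 8.4.

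**The gain is small.** One spot reading at day 7 would seldom catch an episode, whereas the CGM gives about 4 × 24 × 7 = 672 readings in a week. Diabetes and recent anti-diabetic drugs are excluded. Section 13.1 (Safety of Intranasal Insulin) reports no glucose change at doses up to 40 IU four times daily for two months, apart from one mild case at 52 mg/dl. Adverse events are collected at Visit 4 and at week 2. All of this stands, and it limits the weight of the point. The sponsor could restore consistency by narrowing 13.2 instead, but would then have no glucose data in the first three weeks on the combination.

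**Stronger readings that a reader might infer.** One is that a participant could start empagliflozin with no kidney result at all. The documents do not support this: 6.1 requires labs for everyone, 6.3 item 7 cannot be met without a result, 8.2 requires all criteria to be met before baseline, and footnote 2 applies only where evaluations have been done. Another is that nothing stops a person with eGFR below 45 from being randomised. That also goes too far: a physician would have to call such a value clinically insignificant despite the caution in 13.1. What is missing is the numeric threshold and a clear limit on the age of the result.

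**Conclusion.** The point holds as two mismatches between Section 13 and the operative parts of the protocol.

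- **Glucose:** no measure is scheduled at Visit 4, against a commitment to all visits. The shortfall is one reading per participant (60 in all, 15 in the combination arm). First on-drug data come at about day 21 instead of day 7. CGM covers Visit 5 in substance, and Visit 2 precedes treatment, so Visit 4 is the gap that matters.
- **Kidney:** the eGFR limit of 45 is not an eligibility criterion, the existing stop is discretionary, and the waiver wording leaves open results up to 12 months old. The documents do not say how many participants would use the waiver, so no number affected can be given.

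The figures rest on equal allocation, 4 weeks of treatment from Visit 3, and the CGM week being the last treatment week. The hypoglycaemia risk is low. The point concerns participant protection and consistency; it does not show bias in the comparison of serious adverse events.

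**What to change.** 1. Add a point-of-care glucose reading at Visit 4 to Section 8.4 and Table 4, and reword 13.2 so that CGM is the stated method at Visits 2 and 5.
2. Add eGFR<45 mL/min/1.73m² as an exclusion in Section 6.4.
3. State in 8.1 and in footnote 2 of Table 4 that the screening waiver does not cover safety labs, including kidney function, and require a current result to be reviewed before dispensing at Visit 3. For participants who skip screening, draw these labs at Baseline Visit 1, one week earlier, and mark them there under footnote 3.

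The cost is one fingerstick per participant at an existing visit (60 readings), one earlier blood draw for participants whose screening is waived, and possibly a few exclusions for low eGFR, a number that the documents do not give. The rest is wording.
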